1.2. Schema

Abbreviations: AD: antidepressant treatment as specified in ATRQ; DB: double blind; OL: open label; TRD: treatment-resistant depression

1. Non-response at the end of the screening phase is based on improvement in the Montgomery-Asberg Depression Rating Scale (MADRS) total score from Week 1 to Day 1 and the MADRS total score on select screening MADRS assessments
2. With or without standard of care

1.3. Schedule of Activities (SoA)

Screening and Double-blind Phases

Phase	Screening							Double-blind									
	Week	1	2	Optional weeks for tapering/DC ^a		2-week antidepressant-free period ^b		1		2		3		4			
Day						Day -14 to -8	Day -7 to -1	1	2	4	8	11	15	18	22	25	28/EW
Visit Window (days)		±2		±2		±2	±2		+2	±1	±1	±1	±1	±1	±1	±1	±1
Visit	1.1	1.2 ^c	1.3	1.4	1.5	1.6 ^c	1.7	2.1	2.2	2.3	2.4	2.5	2.6	2.7	2.8	2.9	2.10
Clinic visit (C) or Telephone contact (TC)	C	C	C/TC ^a	C/TC ^a	C/TC ^a	C	C	C	C	C	C	C	C	C	C	C	C
Study Procedure																	
Screening/Administrative																	
Informed consent (ICF)	X																
ICF for optional pharmacogenomic research samples	X																
Demographics	X																
Medical and psychiatric history	X																
Employment Status	X																
Inclusion/exclusion criteria ^d	X							X									
MINI	X																
IDS-C ₃₀	X																
MGH-ATRQ	X																
SAFER Interview		X															
Prestudy therapy	X																
Preplanned surgery/procedure(s)	X																
Height	X																
Study Intervention Administration																	
Randomization								X ^d									
Practice session for use of nasal spray device								X ^e									
Dispense/administer study intervention								X		X	X	X	X	X	X	X	
Study intervention accountability								X		X	X	X	X	X	X	X	

Phase	Screening								Double-blind									
	Week	1	2	Optional weeks for tapering/DC ^a			2-week antidepressant-free period ^b		1		2		3		4			
Day							Day -14 to -8	Day -7 to -1	1	2	4	8	11	15	18	22	25	28/EW
Visit Window (days)		±2					±2	±2		+2	±1	±1	±1	±1	±1	±1	±1	±1
Visit	1.1	1.2 ^c	1.3	1.4	1.5		1.6 ^c	1.7	2.1	2.2	2.3	2.4	2.5	2.6	2.7	2.8	2.9	2.10
Clinic visit (C) or Telephone contact (TC)	C	C	C/TC ^a	C/TC ^a	C/TC ^a		C	C	C	C	C	C	C	C	C	C	C	C
Study Procedure																		
Efficacy Assessments																		
MADRS (7-day recall), video teleconferencing	X	X ^{f,g}					X ^g	X ^{g,h}	X ^{g,h}			X ^g		X ^g		X ^g		X ^g
MADRS (24-hour recall), video teleconferencing												X ⁱ						
CGI-S	X								X ^e	X		X ^e		X ^e		X ^e		X
PHQ-9 (patient-reported)							X		X ^e				X ^e					X
Safety Assessments																		
Physical examination	X								X ^e									X
Vital signs predose if applicable (blood pressure, heart rate, temperature)	X						X	X ^h	X	X	X	X	X	X	X	X	X	X
Vital signs postdose (blood pressure, heart rate) ^j									X		X	X	X	X	X	X	X	
Weight	X																	X
12-lead ECG	X								X ^e									
C-SSRS: Baseline/Screening version	X																	
C-SSRS: Since last visit version (predose on dosing days)		X	X	X	X		X	X ^h	X ^e	X	X	X	X	X	X	X	X	
Patient's awareness of treatment arm assignment scale																		X
Clinical Laboratory Tests																		
TSH	X																	
HbA1c	X																	
Lipid panel (fasting)		X																
Hematology, chemistry	X									X ^e								
Urinalysis	X									X ^e								
Drug screen (urine)	X								X ^e									

Phase	Screening								Double-blind									
	Week	1	2	Optional weeks for tapering/DC ^a			2-week antidepressant-free period ^b		1		2		3		4			
Day							Day -14 to -8	Day -7 to -1	1	2	4	8	11	15	18	22	25	28/EW
Visit Window (days)		±2		±2			±2	±2		+2	±1	±1	±1	±1	±1	±1	±1	±1
Visit	1.1	1.2 ^c	1.3	1.4	1.5		1.6 ^c	1.7	2.1	2.2	2.3	2.4	2.5	2.6	2.7	2.8	2.9	2.10
Clinic visit (C) or Telephone contact (TC)	C	C	C/TC ^a	C/TC ^a	C/TC ^a		C	C	C	C	C	C	C	C	C	C	C	C
Study Procedure																		
Serum pregnancy test (women of childbearing potential)	X																	
Urine pregnancy test (women of childbearing potential)									X ^e				X					X
Pharmacokinetic Evaluations																		
Blood sample collection									X ^k									
Biomarker Evaluations																		
Blood sample collection									X ^l									X ^l
Pharmacogenomics (DNA and RNA)																		
Blood sample collection									X ^l									
Ongoing Participant Review																		
Concomitant therapy	X	X		X		X		X	X	X	X	X	X	X	X	X	X	X
Adverse events	X	X		X		X		X	X	X	X	X	X	X	X	X	X	X
Other																		
Menstrual cycle tracking (start date of last menstrual period prior to study visit)	X								X									X
Patient's awareness of treatment arm assignment scale																		X

Footnotes:

Abbreviations: C: clinic visit; CGI-S: Clinical Global Impression – Severity; C-SSRS: Columbia Suicide Severity Rating Scale; DC: discontinue; DNA: deoxyribonucleic acid; ECG: electrocardiogram; EW: early withdrawal; HbA1c test: glycated hemoglobin test; IDS-C₃₀: Inventory of Depressive Symptomatology Clinician-rated, 30-item scale; MADRS: Montgomery-Asberg Depression Rating Scale; MGH-ATRQ: Massachusetts General Hospital - Antidepressant Treatment History Questionnaire; MINI: Mini-International Neuropsychiatric Interview; PHQ-9: Patient Health Questionnaire 9 item; RNA: ribonucleic acid; SAFER: State vs. Trait, Assessability, Face Validity, Ecological Validity, Rule of Three P's; TC: Telephone contact; TSH: thyroid-stimulating hormone

a. After completion of the SAFER Interview and confirmation it was passed, participants who are continuing in the Screening Phase will discontinue all current medication(s) being used for depression treatment, including adjunctive/augmentation medications, prior to the start of the mandatory 2-week antidepressant-free period. If clinically indicated, a participant's current antidepressant treatment(s) may be tapered and discontinued per the local prescribing information or clinical judgment; additional, optional weeks are available in the Screening Phase to allow tapering/discontinuation prior to the start of the 2-week antidepressant-free

period. During tapering/discontinuation, a clinic visit or telephone contact for collection of C-SSRS, adverse events and concomitant therapies should be performed weekly. If the additional weeks are not required, the applicable visit (ie, Visit 1.3, 1.4, 1.5) should be omitted.

- b. All participants must have a 2-week (± 2 days) antidepressant free period in the Screening Phase just prior to randomization at Visit 2.1. For participants not taking any antidepressant medications at the start of screening, the mandatory 2-week antidepressant free period may start at entry. However, the screening phase will be at least 3 weeks in duration to ensure required procedures are completed.
- c. For participants not taking any antidepressant medications at study entry (the start of screening), the mandatory antidepressant free period may start at entry (Visit 1.1). In this scenario only, the following visits would be required: Visits 1.1, 1.2, 1.6, and 2.1.
- d. Minimum criteria for the availability of documentation supporting the eligibility criteria are described in Source Documentation in Appendix 3, Regulatory, Ethical, and Study Oversight Considerations. Verify inclusion/exclusion criteria before randomization of each participant.
- e. Predose (if applicable) and at the actual dosing day. On Day 1 performed pre-randomization.
- f. Must be completed prior to start of tapering or discontinuation of current antidepressant treatment.
- g. The MADRS should be administered no more than 2 days prior to the subject's targeted (not actual) clinic visit date (except Visit 2.1, which is within 1 day prior). If performed on the day of the scheduled clinic visit with an intranasal treatment session, the MADRS must be performed prior to the intranasal treatment session.
- h. If Visit 1.7 and Visit 2.1 are performed on the same day, Visit 1.7 procedure can be omitted (ie, will be performed only as part of Visit 2.1).
- i. The Day 2 MADRS assessment must be administered within the Day 2 to Day 4 window and prior to Day 4 intranasal treatment session.
- j. Performed at $t = 40$ minutes and $t = 1.5$ hours postdose, $t = 0$ is the time of the first spray of nasal spray study medication.
- k. Collected at $t = 40$ minutes and $t = 2$ hours postdose, where $t = 0$ is the time of the first spray of nasal spray study medication.
- l. The pharmacogenomic samples (DNA and RNA) should be collected at the specified time point predose under fasting condition, however, if necessary the sample may be collected at a later visit (predose, fasting) without constituting a protocol deviation.

For Participants Receiving Esketamine: Open-label Treatment/Observation Phase and Follow-up Phase

Phase	Open-label Treatment/Observation Phase														Follow-up		
Week	5		6		7		8		9	10	11	12	13	14	15	16	~ 1 week after last visit
Day	28	31	35	38	42	45	49	52	56	63	70	77	84	91	98	105	-
Visit window	±2	±2	±2	±2	±2	±2	±2	±2	±3	±3	±3	±3	±3	±3	±3	±3	
Visit	3.1	3.2	3.3	3.4	3.5	3.6	3.7	3.8	3.9	3.10	3.11	3.12	3.13	3.14	3.15	3.16	4.1
Clinic visit (C)	C	C	C	C	C	C	C	C	C	C	C	C	C ^a	C	C ^a	C	C
Study Intervention Administration																	
Recommended dosing frequency	Twice weekly ^b								Weekly ^b				Weekly or every other week ^b				
Dispense/administer study intervention	X	X	X	X	X	X	X	X	X	X	X	X	X	X	X	X	
Study intervention accountability	X	X	X	X	X	X	X	X	X	X	X	X	X	X	X	X	
Efficacy Assessments																	
MADRS (7-day recall): video teleconferencing, permitted window of -2 days			X		X		X		X	X	X	X	X	X	X	X	
CGI-S		X	X	X	X	X	X	X	X	X	X	X	X	X	X	X	
Safety Assessments																X	
Physical examination																X	
Vital signs predose (blood pressure, heart rate, temperature)	X ^c	X	X	X	X	X	X	X	X	X	X	X	X	X	X	X	
Vital signs postdose (blood pressure, heart rate) ^d	X	X	X	X	X	X	X	X	X	X	X	X	X	X	X		
C-SSRS: Since last visit version	X ^c	X	X	X	X	X	X	X	X	X	X	X	X	X	X	X	
Clinical Laboratory Tests																	
Drug screen (urine)	X							X				X				X	
Urine pregnancy test	X ^c							X				X				X	
Ongoing Participant Review																	
Concomitant therapy	X	X	X	X	X	X	X	X	X	X	X	X	X	X	X	X	
Adverse events	X	X	X	X	X	X	X	X	X	X	X	X	X	X	X	X	

Footnotes: Abbreviations: C: clinic visit; CGI-S: Clinical Global Impression – Severity; C-SSRS: Columbia Suicide Severity Rating Scale; MADRS: Montgomery Asberg Depression Rating Scale

- Only for participants receiving esketamine treatment session scheduled on that visit.
- Dose frequency should not exceed what is recommended.
- If assessment was performed as part of Visit 2.10 (on the same day), duplicate predose assessment is not required.
- For participants receiving esketamine treatment session: Performed at t = 40 minutes and t = 1.5 hours postdose, t = 0 is the time of the first spray of nasal spray study medication.

For Participants Receiving SOC only: Open-label Treatment/Observation Phase and Follow-up Phase

Phase	Open-label Treatment/Observation Phase															Follow-up								
	Week		5		6		7		8		9		10		11		12		13		14		15	
Day	28	31	35	38	42	45	49	52	56	63	70	77	84	91	98	105	-							
Visit window		± 2	± 3	± 3	± 3	± 3		± 3		± 3														
Visit	3.1	3.2	3.3	3.4	3.5	3.6	3.7	3.8	3.9	3.10	3.11	3.12	3.13	3.14	3.15	3.16	4.1							
Clinic visit (C)	C	C	C	C	C	C	C	C	C	C	C	C		C		C	C							
Study Procedure																								
Efficacy Assessments																								
MADRS (7-day recall): video teleconferencing, permitted window of -2 days			X		X		X		X	X	X	X		X		X	X							
CGI-S	X ^a	X	X	X	X	X	X	X	X	X	X	X		X		X	X							
Safety Assessments																	X							
Physical examination																								
Vital signs (blood pressure, heart rate, temperature)	X ^a	X	X	X	X	X	X	X	X	X	X	X		X		X	X							
C-SSRS: Since last visit version	X ^a	X	X	X	X	X	X	X	X	X	X	X		X		X	X							
Clinical Laboratory Tests																								
Drug screen (urine)	X								X				X			X								
Urine pregnancy test	X ^a							X				X			X		X							
Ongoing Participant Review																								
Concomitant therapy	X	X	X	X	X	X	X	X	X	X	X	X		X		X	X							
Adverse events	X	X	X	X	X	X	X	X	X	X	X	X		X		X	X							

Footnotes:

Abbreviations: C: clinic visit; CGI-S: Clinical Global Impression – Severity; C-SSRS: Columbia Suicide Severity Rating Scale; MADRS: Montgomery-Asberg Depression Rating Scale; SOC: standard of care

a. If assessment was performed as part of Visit 2.10 (on the same day), duplicate predose assessment is not required.

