- receive open-label esketamine nasal spray
 - If clinically indicated based on the investigator's judgment, participants receiving open-label esketamine nasal spray treatment can also receive standard-of-care treatment for depression. The decision to receive open-label esketamine must be made at the start of the open-label treatment/observation phase, participants who chose to not receive esketamine (to be observed only) will not be allowed to start open-label esketamine treatment during this phase.
- choose to be observed only (ie, no esketamine nasal spray treatment sessions) and receive standard-of-care treatment for depression. Participants who choose to be observed only will not be allowed to switch to the open-label esketamine nasal spray arm during the open-label treatment/observation phase.

Evaluations that will be performed during this phase are outlined in the Schedule of Activities.

Participants in this phase who have opted to receive open-label esketamine will receive 56 mg on Day 28 regardless of the participant's study drug/dose assignment in the double-blind phase. Subsequent doses can remain the same or be adjusted (56 mg or 84 mg) based on efficacy and tolerability. The recommended dosing frequency is as follows:

- Weeks 5 to 8: twice weekly (maximum)
- Weeks 9 to 12: once weekly
- Weeks 13 to 16: weekly or every other week. Dosing frequency will be based on clinical judgment and should be individualized to the least frequent dosing to maintain remission/response.

The participant will self-administer esketamine nasal spray under the direct supervision of a healthcare provider during a treatment session at all treatment visits. A treatment session consists of nasal administration of the study medication and post-administration observation. On all dosing days, all participants must remain at the clinical site for post-administration observation until at least 2 hours postdose. After receiving a treatment session, participants are not to engage in potentially hazardous activities, such as driving a motor vehicle or operating machinery, until the next day after a restful sleep. See Section 6, Study Intervention Administered, for blood pressure monitoring guidance on nasal spray treatment session days.

If a participant discontinues the open-label treatment/observation phase for reasons other than withdrawal of consent, the participant will proceed to the follow-up phase.

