5.5.10. Efficacy Data in the Open-Label Treatment or Observation Phase

The summaries will be provided for the open-label analysis set and observation analysis set, separately. Descriptive statistics of the actual values and the change from baseline to each post baseline time point in the double-blind and open-label treatment or observation phase, will be presented for MADRS total score and CGI-S score.

Means and mean changes from baseline (+/- SE) over time will be presented graphically for MADRS total score during double-blind phase and open-label treatment or observation phase.

The number and percentage of participants who achieve remission based on MADRS total score, achieve response based on MARDS total score will be summarized at each time point during the double-blind phase and open-label treatment or observation phase by intervention group.

Remission and response rates based on MARDS total score will be plotted for the double-blind phase and open-label treatment or observation phase.

A frequency distribution over time of the CGI-S scores will be provided for the double-blind phase and open-label treatment or observation phase by intervention group.

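### Open-label Day 84 and Day 98 efficacy summaries come from an outcome-selected subset and are not comparable with Days 77, 91 and 105

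*Protocol*

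**What the plan says.** Protocol 1.3, schedule for participants receiving esketamine: in the clinic-visit row only Visits 3.13 and 3.15 carry a footnote marker, and the first footnote reads "Only for participants receiving esketamine treatment session scheduled on that visit". Visits 3.12, 3.14 and 3.16 (Days 77, 91 and 105) have no such condition. The MADRS row, "MADRS (7-day recall): video teleconferencing, permitted window of -2 days", has a plain mark at 3.13 and 3.15.

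Protocol 4.1 sets the dosing frequency: "Weeks 13 to 16: weekly or every other week". The choice rests on clinical judgment and "should be individualized to the least frequent dosing to maintain remission/response".

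SAP 5.1.2, Table 3 lists Day 84 (open-label days 54-60) and Day 98 (days 68-74) as analysis visits for MADRS and CGI-S. SAP 5.5.10 plans plots ("Means and mean changes from baseline (+/- SE) over time will be presented graphically for MADRS total score during double-blind phase and open-label treatment") and rates (participants who "achieve response based on MARDS total score will be summarized at each time point during the double-blind phase and open-label treatment or observation phase"), and adds that "Remission and response rates based on MARDS total score will be plotted for the double-blind phase and open-label treatment or observation phase". It states no denominator for the rates, no split by dosing frequency, and no rule for visits that are absent by design.

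**The concern.** Whether a participant is assessed at Day 84 or Day 98 depends on dosing frequency, and dosing frequency depends on how the participant is doing. The planned curve would move from everyone still in the phase (Day 77), to those dosed that day (Day 84), back to everyone (Day 91), and so on. A difference between neighbouring points could then reflect who was measured rather than any change in depression. This happens in the weeks when dosing may be spaced out, where a reader may look for loss of effect.

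The SAP handles similar situations elsewhere. For standard-of-care-only participants, Table 4 has no Day 84 or Day 98 and widens the neighbouring MADRS windows (Day 77 to 47-57, Day 91 to 58-71). SAP 5.6.3.1 limits open-label vital-sign summaries over time to dosing days. Open-label efficacy has no equivalent provision.

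**Working it through.** The plan gives no figure for this point, so there is none to reproduce.

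**1. Can neighbouring visits fill the gap?** Open-label day = study day − 27, so Day 84 is day 57 and Day 98 is day 71. With the ±3-day visit window these become 54-60 and 68-74, exactly the Table 3 windows. Day 91 visits fall on days 61-67 and Day 105 visits start at day 75, so they do not fill the gap. One exception is possible. If the 2-day MADRS allowance counts back from an actual visit that is already 3 days early, the rating falls on day 61 − 2 = 59 or 75 − 2 = 73 and would be labelled Day 84 or Day 98.

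**2. Who is scheduled?**

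| Pattern in Weeks 13-16 | Day 84 | Day 98 |
|---|---|---|
| Weekly throughout | yes | yes |
| Every other week counted from Day 77 (dosed Days 91, 105) | no | no |
| Weekly to Day 91, then every other week | yes | no |
| Every other week counted from Day 84 (dosed Days 84, 98) | yes | yes |

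**3. Size of the shift in the mean.** Let f be the share of those still in the phase who are not scheduled at the visit. Hold outcomes constant over time.

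- Full-set mean = (1 − f) × mean(seen) + f × mean(not seen).
- Displayed mean at Day 84 or 98 = mean(seen).
- Shift = f × [mean(seen) − mean(not seen)].

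The documents give neither f nor the gap. The values below are assumptions.

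| Gap, seen minus not seen (MADRS points) | f = 20% | f = 35% | f = 50% |
|---|---|---|---|
| +6 | +1.2 | +2.1 | +3.0 |
| 0 | 0 | 0 | 0 |
| −4 | −0.8 | −1.4 | −2.0 |

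**4. Size of the shift in rates.** Displayed rate = [true rate − f × rate(not seen)] / (1 − f). For illustration I take the end-point rates that Protocol 2.2 reports for the earlier long-term open-label study TRD3004 (response 76.5%, remission 58.2%). Using them here is an assumption.

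- Response, assuming 95% among those not seen: (0.765 − 0.20 × 0.95)/0.80 = 71.9%; f = 35% gives 66.5%; f = 50% gives 58.0%.
- Remission, assuming 85% among those not seen: (0.582 − 0.20 × 0.85)/0.80 = 51.5%; f = 35% gives 43.8%; f = 50% gives 31.4%.

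**5. Denominator.** The rates above use participants assessed at the visit. If the whole open-label set were the denominator, the rates would fall even with identical outcomes: 76.5% × (1 − f) = 61.2%, 49.7% and 38.3% for f = 20%, 35% and 50%. SAP 5.5.10 does not say which denominator applies.

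**The case against.** The strongest counter-argument is that the condition sits on the clinic-visit row, while the MADRS is done by video and its marks at 3.13 and 3.15 carry no footnote. It might therefore still be due from participants without a session. This cannot be excluded. However, the dispensing, accountability and post-dose vital-sign rows also show plain marks in those columns, and they cannot apply to someone who is not dosed. The more natural reading is that the condition governs the whole visit. The text should settle it.

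A reader might infer that the plan will show a spurious worsening. The documents do not support that as a certainty. It requires participants on the sparser schedule to have lower MADRS scores. The frequency rule makes this plausible, but frequency is a matter of judgment, and some participants doing well may stay on weekly dosing because that is what maintains their response. With no gap there is no shift in means, and with the opposite gap the shift reverses.

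A reader might also infer that everyone on every-other-week dosing is left out at both visits. The table of patterns shows otherwise.

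Finally, the stakes are limited. Protocol section 3 lists no open-label efficacy endpoint, the phase is uncontrolled, and SAP 5.5.10 summarizes the open-label and observation sets separately. All of that stands, and it makes this a reporting matter.

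**Conclusion.** The point holds as one of comparability. On the natural reading of the schedule, the Day 84 and Day 98 MADRS, CGI-S, response and remission summaries describe a subset selected partly on outcome. They should not share one series with Days 77, 91 and 105. An artefactual change is possible and an apparent worsening is plausible. Its direction and size rest on the unscheduled share and the outcome gap, which the documents do not give; the figures above are illustrations only.

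The primary and key secondary analyses, the Day 91 and Day 105 values and the open-label last-visit endpoint are untouched. Setting the shift against the planned 5.4-point difference would mislead, because that figure is the randomized Day 28 drug-placebo difference, which this issue cannot affect. Correcting the plan is a cheap improvement to descriptive reporting.

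**What to change.** In SAP 5.5.10:

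- For Weeks 13 to 16, present the full open-label-set means, response, remission and CGI-S series at the visits scheduled for all: Days 77, 91 and 105.
- Show Days 84 and 98 only in a separate display labelled *participants with a dosing session at that visit*, alongside the same participants' Day 77, 91 and 105 values.
- Use participants assessed at each visit as the denominator for rates, and show N.

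In the Protocol 1.3 esketamine schedule, state whether the video MADRS is due at Visits 3.13 and 3.15 when no session is scheduled. If it is collected from everyone, the restriction on the MADRS series is unnecessary.

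The cost is SAP wording and one schedule clarification, with no added visits or ratings. The downside is two fewer points on the full-set descriptive plot.
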